Whether this sleep timing intervention works in actual older night workers, as opposed to participants in lab studies, remains to be tested. We therefore will field test, in older night workers (age 50-65 years), the sleep timing intervention that we have developed in laboratory studies; we will examine the **efficacy** of this intervention in improving sleep duration and quality, as well as performance and alertness across 3 night shifts. We will also conduct a survey study among a large group of older shift workers to examine the factors that influence their ability to adopt such a schedule. Finally, we will have participants from both studies take part in focus groups where the **feasibility** and **acceptability** of the afternoon-evening sleep intervention will be examined. To evaluate the efficacy, feasibility, and acceptability of an 8-h afternoon-evening sleep schedule in the field/real world, our study will address the following Aims:

1. Test the hypothesis that older night shift workers scheduled to an 8-h afternoon-evening sleep episode will sleep longer and have fewer sleep interruptions than those randomized to an *ad lib* sleep/control condition.
2. Test the hypothesis that older night shift workers scheduled to an 8-h afternoon-evening sleep episode will show greater subjective and objective alertness on night shifts compared to those randomized to an *ad lib* sleep/control condition.
  - 2a. Conduct exploratory analyses to examine whether older night workers scheduled to an 8-h afternoon-evening sleep episode show reduced physiological stress (cortisol), reduced subjective stress and fatigue, and improved mood and quality of life compared to those randomized to an *ad lib* sleep/control condition.
  - 2b. Conduct exploratory analyses to compare an 8-h afternoon-evening sleep schedule to an 8-h free sleep

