The Intervention Block is similar to the Baseline Block, consisting of at least three consecutive 8-h night shifts, with the participants wearing an activity monitor, maintaining a daily sleep e-diary, and rating alertness, mood and attention three times per night shift using a mini iPad provided by the investigators. At the end of the first night shift, the participant will be told about their randomization group. In the control group (Group A), participants will not be given any instructions about the timing or duration of their sleep, but will be instructed to follow their usual night shift sleep routine. In the 8-h afternoon-evening sleep intervention group (Group B), participants will be instructed to go to bed between 13:00 and 14:00 (depending on their individual commute time) and to remain in bed attempting to sleep for 8 hours (until 21:00-22:00) before the next two night shifts. In the 8-h free sleep group (Group C), participants will be instructed to remain in bed for 8 continuous hours before the next two night shifts, but will not be given any instruction regarding which 8 hours they should sleep. Immediately following the last night shift, the participant will have the option to take a saliva sample to measure their stress level (cortisol), and they will complete a follow-up questionnaire where their fatigue, recovery, stress, and quality of life will be reassessed to investigate any exploratory short-term changes resulting from the intervention schedule. After completion of the two blocks, the participant will send back the activity monitor and iPad in a prepaid secured return package by mail or an investigator will arrange to meet with the participant to retrieve the activity monitor, iPad, and cortisol sample. Within 3 months after completion of the study blocks the participant will be invited to take part in a virtual Focus Group by secure videoconferencing (via HIPAA-compliant & MGB-approved Zoom).

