## VI. BIOSTATISTICAL ANALYSIS

### VI. a) Data variables, b) Study endpoints, c) Statistical methods

**Analysis of objective sleep duration and quality, and subjective sleep quality in the Field Trial.** Sleep data will be calculated in all participants from both blocks (Baseline vs. Intervention) using actigraphy. Duration of sleep (total sleep time, TST), number of awakenings, fragmentation index (FI) during the major sleep episode and subjective sleep quality from the e-diaries may be used as outcome measures to address Aim 1. After descriptive analyses, we may use linear and generalized linear mixed models to analyze main and interaction effects for factors condition (randomization group: ad lib sleep, 8-h afternoon-evening sleep, or 8-h free sleep) and shift (Baseline: B-Night 2, B-Night 3; Intervention: I-Night 2, I-Night 3). To account for inter-individual differences, we may incorporate into our statistical model a random intercept statement allowing for means to vary between participants. We will compare within subjects (shift) and between groups (condition).

**Field Trial analysis of performance and subjective alertness (Aim 2).** Each of the tests will be administered using an iPad app. Initial processing of tests will be calculated automatically (e.g., exact time of administration, scoring of alertness scales; mean and median reaction time; number of lapses, shortest (fastest 10%) and longest (slowest 10%) reaction times on PVT]. Following the descriptive measures, analyses of RT and lapses and subjective alertness data may be performed using linear and generalized linear mixed models to analyze main and interaction effects for factors condition (randomization group, as above) and shift (as above) with participant as a random effect.

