#### **VI.d. Power analysis**

For the Field Trial we plan to enroll up to 100 participants, with at least 25 participants per group for three groups including A) control group (ad lib sleep); B) 8-h afternoon-evening sleep timing group; C) 8-h free sleep group. For the Shift Worker Survey, we aim to enroll up to 1,000 participants. In the Focus Groups we plan to enroll up to 60 participants, ~30 participants who complete the Field Trial and ~30 participants who complete the Shift Worker Survey.

Our sample size calculations for the Field Trial are based on the preliminary data from our laboratory study (6) comparing the ad lib sleep group with the 8-h scheduled afternoon-evening sleep group, and using total sleep time (TST) and Fragmentation Index (FI) after 2 nights as the outcome measures of interest. For TST, 25 participants per group will give us the power to detect a difference of as few as 78 minutes between groups ( $\alpha=0.05$ ,  $\beta=0.9$ , assumed  $\sigma=84.4$  min), a difference much smaller than that observed in our preliminary study ( $221.4 \pm 84.4$  vs.  $403 \pm 58.5$  min). For FI, 25 participants per group will give us the power to detect a difference of 37 in the fragmentation index (assumed  $\alpha=0.05$ ,  $\beta=0.9$ , assumed  $\sigma=39.9$ ), a smaller difference than that observed in our preliminary study ( $73.3 \pm 39.6$  vs.  $35.2 \pm 20.03$ ).

Our sample size calculations for the Shift Worker Survey are based on multivariable analysis. With at least 500 participants, we will have 90% power to detect an odds ratio of 1.51 for any continuous factor with one standard deviation difference, or 2.10 for any binary factor (yes vs. no) with a two-sized z-test at alpha=0.05 level, assuming the variance explained by other factors in the same model is 0.2.

Our sample size of 30 participants for the Focus Groups were selected to solicit qualitative information from approximately half of the Field Trial participants who were randomized to a sleep intervention, and from approximately 10% of the Shift Worker Survey participants who report being unable to adopt an 8-h sleep schedule when working night shifts.

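### The Aim 1 analysis names no deciding contrast: it should state B minus A on the two intervention nights, adjusted for baseline, with a covariance that separates the two blocks

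*Combined protocol and SAP*

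**What the plan says.** Write A for the ad lib control, B for the scheduled 8-h afternoon-evening group and C for the 8-h free sleep group.

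- **Hypothesis (II. Specific Aims, Aim 1).** Workers in B "will sleep longer and have fewer sleep interruptions than those randomized to an" ad lib control condition. Two groups are named, but no nights.
- **Sample size (VI.d).** It rests on laboratory data "comparing the ad lib sleep group with the 8-h scheduled afternoon-evening sleep group", with total sleep time (TST) and Fragmentation Index (FI) measured after two nights: "25 participants per group will give us the power to detect a difference of as few as 78 minutes between groups".
- **When groups can differ (V, Intervention Block).** "At the end of the first night shift, the participant will be told about their randomization group". The sleep instruction then covers the two remaining shifts.
- **Analysis (VI.a–c, Aim 1 paragraph).** "we may use linear and generalized linear mixed models to analyze main and interaction effects for factors condition" (three levels) and shift (four levels: nights 2 and 3 of each block). Further, "we may incorporate into our statistical model a random intercept statement allowing for means to vary between participants". The comparison itself is given only as "We will compare within subjects (shift) and between groups (condition").
- **Outcomes (same paragraph).** TST, awakenings, FI and "subjective sleep quality from the e-diaries may be used as outcome measures to address Aim 1".
- **Allocation (IV.c).** Randomisation is done by gender. Gender is in no Field Trial model.

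**The concern.** The listed effects answer different questions. The condition effect, taken over all four nights, averages in two nights on which the groups have not yet been treated differently. The shift effect is a within-participant change, not a randomised comparison. The condition-by-shift interaction has 6 degrees of freedom and does not isolate B against A. The analysis section does not say which of these, for which pair of groups and nights, decides Aim 1. The stated 90% power therefore belongs to a comparison that the section does not name, and the choice could be made after the data are seen.

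There is a second issue inside the model. The baseline and intervention blocks are separate weeks, so two nights in the same block may well be more alike than two nights in different blocks. A single random intercept cannot represent that, and the contrast that crosses blocks is the one whose standard error suffers.

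**Working it through.** **Inputs.** From VI.d: 25 per group; TST difference 78 min, SD 84.4; FI difference 37, SD 39.9; alpha 0.05; 0.9 taken as power. Assumed, because the documents give none: correlation *w* between nights in the same block and *b* between nights in different blocks.

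**1. The plan's own figure.** n = 2(1.96 + 1.2816)² SD²/difference².
- TST: 21.01 × 84.4²/78² = 24.6, so 25.
- FI: 21.01 × 39.9²/37² = 24.4, so 25.

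Power by noncentral t is 89.3% and 89.5%. The sample size reproduces as a two-sided B against A comparison.

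**2. What each effect would deliver.** Let the true B minus A difference be 78 min on both intervention nights and 0 at baseline, and let s² be the single-night variance.
- Four-night condition effect: expected difference (0 + 0 + 78 + 78)/4 = 39 min; variance per participant s²(1 + w + 2b)/4.
- Intervention-night mean: expected 78; variance s²(1 + w)/2.
- The same, baseline-adjusted: variance s²(1 + w)/2 × (1 − r²), with r = 2b/(1 + w).

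The standard error of B minus A is √(2 × variance/25). Example at w = b = 0.2: variance 7123.4 × 1.6/4 = 2849, SE 15.1, and 39/15.1 = 2.58, so power is 72%. At w = b = 0.7: SE 21.0, ratio 1.86, power 45%.

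The next table gives power in % (noncentral t, 72 df; 70 df when adjusted). The first figure takes 84.4 as the SD of a single night. The bracketed figure takes it as the SD of a two-night mean, so that s² = 84.4² × 2/(1 + w).

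| w / b | Four-night condition | Intervention nights | Baseline-adjusted |
|---|---|---|---|
| 0.2 / 0.2 | 72 [51] | 99 [90] | 99 [93] |
| 0.5 / 0.5 | 53 [42] | 96 [90] | >99 [99] |
| 0.7 / 0.7 | 45 [39] | 94 [90] | >99 [>99] |
| 0.5 / 0.3 | 60 [49] | 96 [90] | 98 [94] |
| 0.7 / 0.3 | 57 [50] | 94 [90] | 96 [93] |

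For FI the four-night effect would estimate 18.5 of 37, with about 72–45% [51–40%] power at equal correlation 0.2–0.7.

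**3. Random intercept alone.** The change from baseline to intervention (mean of two nights minus mean of two nights) has true variance s²(1 + w − 2b) per participant. A random-intercept model judges it against the pooled within-participant mean square. That mean square averages two within-block contrasts, each s²(1 − w), and the block contrast: s²[2(1 − w) + (1 + w − 2b)]/3.
- 0.5/0.3: assumed 0.633 s², true 0.9 s². The SE is too small by √(0.9/0.633) = 1.19, and 1.96/1.19 = 1.64, so type I error is about 10%.
- 0.7/0.3: assumed 0.567 s², true 1.1 s². The factor is 1.39, and 1.96/1.39 = 1.41, so about 16%.
- 0.5/0.5: both are 0.5 s², so 5%.

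Simulation of the baseline-adjusted version (group means equal at baseline, 40,000 null trials per case) gave 8.7%, 13.6% and, at equal correlation, 4.8–4.9%. With a participant-by-block term, or with the baseline mean as covariate, it gave 4.8–5.2%.

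**4. At the laboratory difference.** 403 − 221.4 = 181.6 min. Every test then has about 98% power or more, and only the halved estimate (90.8 min) remains an issue.

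**The case against.** The strongest reply is that the plan already contains the right comparison. The model has interaction effects, the shift levels are labelled Baseline and Intervention, and the Baseline Block paragraph in section V says its sleep measures serve Aim 1. Together these point to a baseline-referenced comparison. This stands: a reader might infer that the plan tests the wrong effect or that the trial is underpowered, and the documents support neither. The 39 min and the 39–72% power apply only if the four-night condition effect is reported as the Aim 1 result. Still, a contrast that can be estimated has not thereby been prespecified.

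Other points that stand:
- Aim 1 does not itself name the intervention nights; they follow from when the group is disclosed. In VI.d, measurement after two nights could mean one sleep episode or two, hence the two SD readings.
- The three-group interaction can reject when only C differs. That is correct behaviour, not an error; it merely does not answer Aim 1.
- One might infer that TST must rank above FI. The documents do not require it: both are powered, and Aim 1 joins longer sleep and fewer interruptions. If both must be shown, each can be tested at 0.05 without a hierarchy.
- The type I error inflation needs unequal correlations, which are assumed. The random intercept is itself only optional in the text.

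**Conclusion.** The concern holds as a gap in specification together with a covariance weakness. No section ties an effect, a pair of groups and a set of nights to Aim 1. The sample size is sound for B against A, and naming the contrast preserves it: about 90% power or more on the intervention nights unadjusted, and about 92% or more adjusted in every case tried (lowest 91.7%, at 0.5/0.2 on the two-night SD reading).

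The cost of leaving it open is conditional. There is a halved estimate and 39–72% power if the condition effect is used. There is a type I error of about 9–10% or 14–16% for the baseline-referenced contrast if only a random intercept is fitted and correlations are 0.5/0.3 or 0.7/0.3; at equal correlation it is about 5%. Baseline adjustment is an efficiency gain of uncertain size: the adjusted variance is 89–32% of the unadjusted at equal correlations of 0.2–0.7, and 84–88% at between-block 0.3. The gain from including gender cannot be quantified from the documents.

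**What to change.** In the Aim 1 paragraph of VI.a–c, replace the optional wording by a commitment:

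- Aim 1 is tested by B minus A averaged over I-Night 2 and I-Night 3, two-sided 0.05, adjusted for baseline, with gender as a factor because allocation uses it.
- Fit this in one of two ways: with the mean of the baseline nights as covariate; or with the planned four-night mixed model, group means set equal at baseline, plus a participant-by-block random term or an unstructured covariance.
- The Aim 1 conclusion does not rest on the four-night condition effect or on change within a group.
- State whether Aim 1 requires both TST and FI (each at 0.05) or either one (with a stated alpha rule). That choice is the sponsor's.

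The cost is a few sentences, slightly more analysis work and about 2 degrees of freedom (baseline and gender). Baseline nights are already recorded and gender is already used for allocation, so no new data are needed. The sample size stays at 25 per group.

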Role of the circadian timing system and prior wake duration on alertness and performance. A proper alignment between the timing of the biological clock and the timing of sleep is critical for optimal waking performance. Human cognitive functioning is modulated by a variety of factors, including the sleep-wake homeostat (elapsed time awake) and the phase (timing) of the circadian pacemaker. The sleep-wake homeostat contributes an approximately linear decline to cognitive function, while the endogenous circadian rhythm contributes a sinusoidal variation over the course of the 24-h day (58-61). Under normal conditions in well-rested individuals, these two systems interact to produce a stable level of cognitive functioning across a ~16h wake episode: in the evening the wake-dependent deterioration of alertness is opposed by the circadian timing system promoting alertness.

Unfortunately for night workers, many studies have shown that the decline in performance and alertness resulting from prior wakefulness is actually amplified during the biological night (60, 61). Therefore, night workers must not only attempt to remain awake at an adverse biological time, but the negative impact of that wakefulness is greater. To make matters worse, after attempting to remain awake all night, the typical night worker starts sleep in the morning following work (62, 63), a biological time at which it is difficult to sustain sleep for an extended duration. Not surprisingly, night workers typically report shorter sleep than their day worker counterparts (40, 42), resulting in even greater levels of sleepiness on the following night.

Furthermore, unlike the day worker who wakes on average 2-3h before reporting to work, night workers are typically awake longer than day workers before reporting to work, resulting in the end of their work occurring after more than 12h awake, reducing even further their ability to remain alert throughout the night shift. We have shown in our laboratory study that evening sleep (before the simulated night shift) combined with enhanced lighting during the latter half of the night shift can improve performance and alertness back to day shift levels (4), while morning sleep still produced significantly impaired performance, likely due to the greater duration of time awake (5).

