### Field Trial outcome variables

Sleep measurements including Total Sleep Time, Fragmentation Index, Wake After Sleep Onset, and Subjective Sleep Quality will be measured during the Baseline block and during the Intervention block. Sleep episodes in all participants will take place at home during off-shift times and will be recorded using wrist actigraphy and daily sleep e-diaries (which will be completed in the first hour after waking from the main sleep episode).

Subjective Alertness During both the Baseline and Intervention blocks, participants will complete an alertness task on the iPad three times per night shift: Once just before the night shift, once during their shift break, and once immediately following the night shift. The alertness assessment will consist of the Karolinska Sleepiness Scale (KSS) and a non-numeric bipolar (sleepy-alert) Visual Analog Scale (VAS).

Sustained Attention During both the Baseline and the Intervention Blocks, participants will complete a psychomotor vigilance task on the iPad three times per night shift: Once just before the night shift, once during their shift break, and once immediately following the night shift. The psychomotor vigilance task (PVT) is a 5-minute validated test of visual reaction time (RT) in which the participant is asked to maintain the fastest possible RTs to a simple visual stimulus.

Subjective Mood During both the Baseline and the Intervention Blocks, participants will complete a mood questionnaire on the Ipad three times per night shift: Once just before the night shift, once during their shift break, and once immediately following the night shift. Non-numeric bipolar (happy-sad) Visual Analogue Scales (VAS) will be used to assess subjective well-being and mood.

Fatigue, Inter-Shift Recovery, Subjective Stress and Quality of life will be assessed by questionnaire on the iPad immediately after the third night shift in the Baseline block and after the third night shift in the Intervention block (151, 152, 124).

Physiological Stress will be assessed by collecting a saliva sample immediately after the third night shift in the Baseline block and after the third night shift in the Intervention block to measure cortisol in subjects who live in the greater Boston area. Cortisol will be assayed in the Brigham Research Assay Core.

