**Exploratory analysis of subjective stress and fatigue, recovery, mood, quality of life, and physiological stress in the Field Trial (Aim 2a).** Scores of acute subjective fatigue, inter-shift recovery, subjective stress, and quality of life will be calculated from the questionnaire administered at the end of Baseline and the end of Intervention. Mood will be assessed from visual analog scales administered three times per shift on nights 2 and 3 in the Baseline and Intervention blocks. Physiological stress will be assessed by analyzing cortisol levels in the optional saliva samples collected immediately after the third night shift in the Baseline and Intervention blocks. We will compare data from the Baseline to data from the Intervention for the three groups using linear and generalized linear mixed model analysis with factors condition (randomization group) and block (Baseline or Intervention) and incorporating a random intercept statement allowing for means to vary between participants.

**Field Trial exploratory analysis of scheduled 8-h afternoon-evening sleep vs. 8-h free sleep (Aim 2b).** We may compare results described above (sleep, performance and alertness, subjective stress, fatigue, recovery, mood, quality of life, and physiological stress) between the two scheduled sleep groups to determine whether the timing of an 8-h sleep episode has a significant impact on any of the outcomes. For this analysis, data from the 8-h free sleep group will first be examined for the time of day at which it occurred. Those participants who self-selected an afternoon-evening sleep episode will be classified with the 8-h afternoon-evening sleep group. We will carry out the analyses described above using linear mixed model analysis with factors condition (randomization group) and block (Baseline or Intervention) or night, incorporating a random intercept statement allowing for means to vary between participants.

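### Aim 2 fixes neither its unit of analysis nor its deciding contrast, and with participant as the only random effect its standard error can be too small whether the three tests per shift are kept as rows or averaged

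*Combined protocol and SAP*

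**What the plan says.** **Data collected.** Section V, Field Trial outcome variables, has three sittings per shift (before, on break, after). For attention, "participants will complete a psychomotor vigilance task on the iPad three times per night shift"; the KSS, the alertness VAS and the mood VAS follow the same pattern.

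**Aim 2 hypothesis (section II).** The afternoon-evening group "will show greater subjective and objective alertness on night shifts compared to those randomized to an" ad lib control condition.

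**Aim 2 model (section VI.a-c).** Initial processing yields, among other things, "exact time of administration, scoring of alertness scales". Reaction time, lapses and alertness may then be analysed, in permissive wording, by linear and generalized linear mixed models. The factors are condition ("randomization group, as above) and shift (as above) with participant as a random effect". Shift has four levels: nights 2 and 3 of Baseline and of Intervention. No time-of-test factor, nested random effect, residual covariance or deciding contrast is named.

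**Aim 2a, exploratory.** "Mood will be assessed from visual analog scales administered three times per shift on nights 2 and 3" of each block. Then: "We will compare data from the Baseline to data from the Intervention for the three groups", with factors condition and block and a random intercept per participant.

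**Aim 2b, exploratory.** The two scheduled-sleep groups are compared "using linear mixed model analysis with factors condition (randomization group) and block (Baseline or Intervention) or night", again with a random intercept.

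**The concern.** A single participant effect treats all of a person's measurements as equally correlated, whichever week or shift they come from. The protocol's own account of sleep and alertness makes that doubtful. The three tests in a shift follow the same preceding sleep, so they probably share a shift-specific deviation (participant-by-shift variance). The two blocks are different weeks, so a person's level may move between them for reasons other than group (participant-by-block variance). Block variance matters most, because the Aim 2 comparison is a change between blocks.

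The plan also leaves out time of test, although it is recorded. Section I.a supports expecting a within-shift change: "The sleep-wake homeostat contributes an approximately linear decline to cognitive function". If tests are rows, that change goes into the residual and inflates the standard error.

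At stake is the p-value for a stated hypothesis. Two analysts could both follow the text, one using rows and one using per-shift means. In a linear model with complete data they would get the same estimate, but they could report different standard errors.

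**Working it through.** **The plan's own figures.** None concerns Aim 2. The Field Trial power statement covers TST and FI only, and it reproduces: n = 2[(1.960 + 1.282) × 84.4/78]² = 24.6, so 25; and 2[(1.960 + 1.282) × 39.9/37]² = 24.4, so 25. Nothing below changes it.

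**Inputs from the documents.** 3 groups, at least 25 per group (25 used), 4 shifts, 3 tests per shift.

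**Assumed inputs.** Total variance 1 with participant share 0.40; block share b (0 to 0.10); shift share s (0 to 0.15); single-test variance e = 0.60 − b − s; no true effect; within-shift trend either nil or 0/0.5/1 total SD at the three tests, common to all groups; balanced complete data.

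**Contrast.** Change from Baseline to Intervention, afternoon-evening minus ad lib (1 df). This is my reading of section II; the plan does not name it.

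**Formulas.**
- True variance of one participant's change: V = 2(b + s/2 + e/6).
- Rows: the random-intercept residual mean square is M = [72(e + 3s + 6b) + 144(e + 3s) + 600e + T]/816. T = 0 without a trend; with it, T = 75 × 4 × 0.5 = 150. The model takes the variance of the change to be 2M/6.
- Averaged per shift: with v = s + e/3, the residual mean square is A = [72(v + 2b) + 144v]/216. The model takes the variance of the change to be 2A/2 = A.
- r = model SE / true SE; rejection rate ≈ 2[1 − Φ(1.96 r)].

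**Worked case, b = s = 0.05, e = 0.50.**
- V = 2(0.05 + 0.025 + 0.0833) = 0.3167.
- Rows, no trend: M = (68.4 + 93.6 + 300)/816 = 0.566; 2M/6 = 0.189; r = √(0.189/0.3167) = 0.77; rejection 13%.
- Rows, trend: M = 612/816 = 0.750; 2M/6 = 0.250; r = 0.89; rejection 8%.
- Averaged: v = 0.2167; A = (22.8 + 31.2)/216 = 0.250; r = 0.89; rejection 8%.

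With this trend, rows and averaging coincide, and both are too liberal.

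**Grid (r, then rejection).**

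| block, shift (%) | rows, no trend | rows, trend | averaged |
|---|---|---|---|
| 0, 0 | 1.00, 5.0% | 1.14, 2.5% | 1.00, 5.0% |
| 0, 5 | 0.92, 7.2% | 1.05, 3.9% | 1.00, 5.0% |
| 0, 15 | 0.80, 11.9% | 0.91, 7.3% | 1.00, 5.0% |
| 5, 5 | 0.77, 13.0% | 0.89, 8.2% | 0.89, 8.2% |
| 5, 15 | 0.69, 17.7% | 0.80, 11.9% | 0.91, 7.5% |
| 10, 5 | 0.67, 18.7% | 0.78, 12.7% | 0.82, 11.0% |
| 10, 15 | 0.61, 23.1% | 0.71, 16.4% | 0.85, 9.8% |

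Simulation (20,000 runs per setting) agrees: with block 5-10% and shift 5-15%, rows give 13.1-23.1% without trend and 8.2-16.3% with it, and averaging gives 7.2-10.9%.

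**Sensitivity at 5%/5%, rows.** Trends of 0, 0.5, 1 and 1.5 SD across the shift give 13, 12, 8 and 4.5%. Participant shares of 20% and 60% give 11% and 17% without trend.

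**Mood, condition-by-block test (2 df), six rows per block.** The numerator mean square has expectation e + 3s + 6b. The residual mean square is [72(e + 3s + 6b) + 150(e + 3s) + 600e + T]/822. At 5%/5% without trend these are 0.95 and 0.567, a ratio of 1.68, and about 17% rejection. Over block 5-10% and shift 5-15%, the range is 17-32% without trend and 9-22% with it. One value per block gives 5%.

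**The case against.** - **Every variance share is assumed.** True. The documents give none, so no rate above is a prediction. With no block or shift variance the row model is exact without a trend and conservative (2.5%) with one.
- **The two omissions may cancel.** They can: at 5%/5% a trend of 1.5 SD brings rows to 4.5%. The trend's size is unknown, though. The Background sentence supports a direction only, and its other half adds a sinusoidal circadian component, so a straight line is a convenience.
- **Any sensible analyst would average.** Perhaps, but the plan does not say so. Averaging removes the participant-by-shift problem, not the participant-by-block one.
- **Silence is not exclusion.** Aim 2 says only that participant is a random effect. The random intercept is spelled out for Aims 1, 2a and 2b and is the natural reading here, but it is an inference.
- **The same-estimate statement is limited.** It needs arithmetic means in a linear model with complete data. It need not hold for medians, a single selected test, or lapses in a generalized model.

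A reader might infer something stronger from the overall 6-df condition-by-shift test, which in simulation rejects 35% as rows against 6% averaged. That is the largest clustering tried, with no trend; with the trend the row figure is 18%. The test also brings in the free-sleep group and night-to-night differences, so it is not the section II comparison.

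**Conclusion.** The point stands as an under-specification with a real error risk. Aim 2 names neither the unit of analysis nor its deciding contrast. If participant-by-block variance exists, the named model gives too small a standard error for the Baseline-to-Intervention contrast under either reading. Rows add a further shortfall if participant-by-shift variance exists, and an omitted time-of-test effect offsets some or all of it.

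Under the stated assumptions (block 5-10%, shift 5-15%), a nominal 5% test rejects 13-23% (rows, no trend), 8-16% (rows, trend) or 7-11% (averaged). The net error in the actual trial could be large or close to nil.

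A reader might conclude that Aim 2 will produce excess false positives, that averaging alone cures the problem, or that the trial is the wrong size. The documents support none of these: the variances are unknown, averaging leaves the block component, and the power statement concerns other outcomes. The mood version applies only if the six ratings per block enter as rows, and that aim is exploratory. The generalized model for lapses was not simulated. This is a cheap improvement that should be made before analysis.

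**What to change.** Name the afternoon-evening versus ad lib difference in change from Baseline to Intervention as the Aim 2 test, then choose one:

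- **(a) One value per shift.** Define it, including how a shift with a missing test is scored. Fit an unstructured covariance across the four nights (or add a participant-by-block effect), with a small-sample correction.
- **(b) Rows.** Add time of test and its interaction with condition as fixed effects, plus random participant-by-block and participant-by-shift effects, with Kenward-Roger or Satterthwaite df for linear models. Average the contrast over the three test times.

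Do not add time of test alone. That removes the offsetting error and leaves the 1-df test at 13-23% for block 5-10%.

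For mood, use one value per block or option (b). For lapses, use the same random effects in the generalized model. If a model fails to converge, analyse one change, or baseline-adjusted change, per participant.

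In simulation, the nested random effects of (b) held the 1-df test at 4.2-5.3% and the per-participant change at 4.7-5.3%. The simulated (b) had no time-by-condition term, which is orthogonal to the contrast in balanced data.

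**Cost.** A few sentences and lines of code; the data, including test time, are already collected. Intervals widen where clustering exists: without trend, by a factor of 1/0.77 = 1.3 at 5%/5% and 1/0.61 = 1.6 at 10%/15%, relative to the row-level random-intercept model. Option (a) gives up the within-shift time course. Option (b) is slightly conservative (about 4%) when a variance component is truly zero.
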